- (2) **Pain inhibition (Aim 2): Pain** is modulated and controlled by central, top-down pain-facilitatory and inhibitory circuits, which can dramatically increase or reduce (respectively) the intensity of a sensation³⁰. The capability to inhibit pain has been shown to contribute to the phenomenon of **pain habituation**. Specifically, painful stimuli administered on a daily basis result in substantially decreased pain ratings^{11;40} (habituation), and this effect has been linked to the activation of pain-inhibitory circuits⁶. The ability to habituate to daily aches and pains likely counteracts the process of sensitization and has been suggested to serve as a protective mechanism against the development of chronic pain^{32;36}. We postulate here that the failure to habituate to repeated (day-to-day) painful stimulation over the course of repeated exposure to a model of experimental insomnia is driven by a progressive deterioration in the capability to inhibit pain, which has previously been shown sensitive to short-term sleep disruption³⁷ as well as to insomnia disorder²¹.

[figure not shown]
Figure 1: Conceptual model of mechanistic pathways underlying the insomnia-pain relationship

In summary, we propose two processes by which repeated exposure to experimentally induced

insomnia promotes chronic pain vulnerability: (1) Increased sensitization of the nociceptive system via inflammatory dysregulation; (2) Decreased habituation to pain via failure of the pain-inhibitory system.

Do we recover from the effects of repeated exposure to experimental insomnia episodes (Aim

3)? Is a single night of good sleep in-between episodes of deficient sleep sufficient to reverse inflammatory and pain-inhibitory system changes? Or are more nights required? This is an important question designed to assess the elasticity or plasticity of systems in their attempt to return to normal functioning after exposure to sleep deficiency. **If these changes are more or less difficult to reverse by good sleep, this finding may urge to focus on the prevention of such changes, rather than treatment after change occurred.**

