Recovery from deficient sleep has been rarely studied, but we and others have shown that after a single episode of sleep restriction or total sleep deprivation, the inflammatory marker IL-6 (plasma and mRNA levels) do not normalize after one night or even two nights of recovery sleep⁴². Furthermore, preliminary data from our ongoing study suggest that the expression of IL-6 by monocytes never fully returns to baseline during brief recovery sleep periods occurring during a longer period of sleep restriction (see **Figure 3**). From this perspective, (and as depicted in **Figure 2**), we expect that during a single night of recovery sleep (typical for insomnia^{31;41}) between successive episodes of experimental insomnia, the ability of inflammatory systems markers to return to baseline will progressively decline, and their sensitizing actions will prevent normalization of pain measures (i.e., pain thresholds and temporal summation of pain). Similarly, we assume that recovery of the pain-inhibitory system will not be fully achieved during a single night of good sleep in-between experimental insomnia episodes, leading to a situation where the next exposure to insomnia ‘hits’ an incompletely recovered system. As depicted in **Figure 2**, we expect that the ability of the pain-inhibitory system to return to baseline will progressively decline during successive recovery sleep periods, leading to less habituation to pain over time, as manifested in a failure to experience supra-threshold pain as less intensive across day-to-day exposure.

Summarizing the importance and implications of the knowledge gained:

- (1) While it has long been known that insomnia is highly comorbid with chronic pain conditions, we still do not have a good understanding of the underlying mechanisms. To our knowledge, this proposal will be the first to investigate the mechanistic roles of two processes that we hypothesize to underlie insomnia-induced pain processing abnormalities: (a) Inflammatory-induced sensitization of the nociceptive system and (b) pain-inhibitory-induced habituation.
- (2) Considering the high life-time prevalence of insomnia and chronic pain, as well as their high comorbidity, mechanistic knowledge is essential for the development of specific targets to prevent or ameliorate pain amplification due to insomnia. As it is unlikely that we will eradicate insomnia in

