To summarize, this proposal has various innovative aspects in the investigation of pain amplification in response to insomnia: (1) Taking a mechanistic approach (inflammatory-induced sensitization, pain-inhibitory induced habituation to pain), rather than continuing to characterize the general association between insomnia (or sleep deficiency in general) and pain. (2) Studying inflammatory and pain-inhibitory systems changes within a real-life model consisting of repeated exposure to experimentally-induced insomnia symptoms, rather than studying changes within short-term models of sleep restriction or deprivation of a few days. (3) Investigating the ability of system changes to recover from repeated exposure to experimentally-induced insomnia symptoms, rather than concentrating only on the effects of deficient sleep.

B3. DESCRIPTION OF RESEARCH PROTOCOL

A. Study Design – Overview, Methods, Procedures

Proposed Research Plan.

The overarching hypothesis of this research is that repeated exposure to experimentally-induced insomnia symptoms increases vulnerability to chronic pain by promoting two processes: (1) sensitization of the nociceptive system via a progressive increase of the inflammatory response and (2) decreased habituation to pain via progressive deterioration of the pain-inhibitory response.

This proposal will implement a research design consisting of 3 repetitions of a 4-day episode with 3 nights of experimentally-induced insomnia symptoms followed by 1 night of recovery sleep, thereby resembling frequently observed sleep patterns in individuals suffering from insomnia. I.e., after an interval of 1 to 3 nights of poor sleep, individuals experience a better night of sleep, likely resulting from a buildup of sleep pressure during the insomnia episode^{31,41}. The protocol will end with 4 nights of recovery sleep, in order to statistically model time to obtain full recovery of the inflammatory and pain-inhibitory system. The study will take place under controlled in-laboratory conditions in the Clinical Research Center, in order to ensure maintenance of sleep-wake schedules and minimize the influence of confounding variables such as food or fluid intake, light exposure, body posture and motor activity. Each protocol includes frequent blood draws, urine collections, and the administration of a complex pain testing battery on 8 out of the 18 in-hospital days.

Study Design.

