This study will employ an intra-individual balanced 2 x 18-day in-hospital protocol (experimental insomnia vs. control sleep condition, see **Figure 8**). The first 2 nights of each 18-day protocol will be adaptation nights, and the 3rd night will serve as the baseline night, with a sleep opportunity of 8 hours (23pm-7am) on all 3 nights. In the experimental insomnia study arm, insomnia symptoms will be induced during the next 3 nights, followed by 1 night of 8-hour recovery sleep (for more details, see model description under Procedures). During nights with insomnia symptom induction, sleep onset will be delayed by 1 hour (midnight 12am), the sleep period (12-6am) will be disrupted by hourly 20 min long awakenings, and sleep offset will be advanced by 1 hour (6am). This episode of 3 nights of experimental insomnia followed by 1 night of recovery sleep will be repeated three times. After the last experimental insomnia episode, participants will have 4 recovery nights. In the control arm of the study, participants will receive an 8-hour sleep opportunity for all 18 nights of the protocol. These 2 arms of the study will be separated by an interval of at least 1 month in order to allow recovery from blood sampling. Monthly separation was chosen to control for potential effects of menstrual phase in women. Depending on the bed occupancy space, participants will stay in a private room in the CRC. If a private room is not available, participants will stay in a double occupancy room with an individual of the same sex (assigned at birth)

Visit 1. Initial screening. All potential participants will have the study explained to them in detail by the PI or another senior member of the research team. If interested, potential participants will sign the informed consent and nursing staff in the Clinical Research Center (CRC) will take vital signs and collect a blood sample. A short battery of screening tests and questionnaires will also be collected in order to assess health status (see **Appendix 1** for blood tests and questionnaires). Potential participants will then be introduced to the web-based, secured diary recording system (REDCap²²) and given an actigraphy watch to take home to estimate sleep-wake habits, for 2 weeks (see **Appendix 1**). These data will be used to verify nightly sleep duration between 7 to 9 hours to be used for eligibility.

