Assessment of Aim 2: Pain-inhibitory response and its relation to indicators of habituation to pain upon repeated episodes of experimentally-induced insomnia symptoms. Analysis will follow the strategy similar to one outlined in Aim 1. To evaluate co-variation of the pain-inhibitory response with indicators of habituation we will first obtain average values of each value for each day, and use the Altman-Bland correlation approach described earlier.

These data will be analyzed using linear mixed model for doubly repeated measures using SAS GLM procedure as described in:

http://support.sas.com/documentation/cdl/en/statug/63033/HTML/default/viewer.htm#statug_glm_sect054.htm.

Assessment of Aim 3: Recovery of the inflammatory and pain-inhibitory response upon

repeated episodes of experimentally-induced insomnia symptoms. The proposed incomplete resolution of inflammatory and pain-inhibitory responses during the recovery nights and the progressive impairment of these responses across insomnia induction episodes will be evaluated using a mixed model approach and utilizing four time points: baseline, and recovery at the end of 1st, 2nd, and 3rd insomnia episode. Recovery response will be further evaluated by comparing effects of a single night of recovery sleep to a set of 3 nights of recovery sleep at the end of the protocol. Data analysis for this aim is similar to data analysis described for Aim 1, but a different set of contrasts need to be defined. Our conjecture is that during the recovery IL-6 drops but does not reach to the level of previous recovery. To test this we will evaluate contrasts that compare IL-6 values at days 3 and 7, 7 and 11 and 11 and 15. Finally, the difference between day 15 and 17 is assumed to be larger than any other difference between sleep restriction and recovery days. To test this we will evaluate the differences between other recovery days (average of days 7, 11, and 15) and day 17. All analysis will be performed using SAS statistical package (version 9.3).

C. Subject Selection

Human Subjects Involvement and Characteristics

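### Aim 3's named test of extra recovery nights pools days that follow fewer insomnia episodes, so it understates the gain if one-night recovery worsens as the plan conjectures

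*Combined protocol and SAP*

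**What the plan says.** All references are to the combined protocol and SAP.

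- **B3, Assessment of Aim 3.** A second look at recovery is described as "comparing effects of a single night of recovery sleep to a set of 3 nights of recovery sleep at the end of the protocol". The expected course for IL-6 is this: "Our conjecture is that during the recovery IL-6 drops but does not reach to the level of previous recovery". The contrasts listed for it are days 3 v 7, 7 v 11 and 11 v 15.
- **Same paragraph.** The plan then says that "the difference between day 15 and 17 is assumed to be larger than any other difference between sleep restriction and recovery days", and continues: "To test this we will evaluate the differences between other recovery days (average of days 7, 11, and 15) and day 17".
- **B2.** The background makes the same prediction: between successive episodes "the ability of inflammatory systems markers to return to baseline will progressively decline". It also asks: "Is a single night of good sleep in-between episodes of deficient sleep sufficient to reverse inflammatory and pain-inhibitory system changes", and whether more nights are needed.
- **B3, Proposed Research Plan.** "The protocol will end with 4 nights of recovery sleep, in order to statistically model time to obtain full recovery".
- **B3, Study Design.** In the control arm, "participants will receive an 8-hour sleep opportunity for all 18 nights of the protocol", so every analysis day has a control counterpart.
- **B3, Assessment of Aim 1.** A piece-wise regression with one knot for the prolonged final recovery is offered as an option. It is not named as the test of one against three nights.

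**The concern.** The expectation concerns days 15 and 17; the test offered for it pools days 7, 11 and 15. Counted by night, days 15 and 17 share the same exposure (three episodes) and differ only in the number of recovery nights. Days 7 and 11 come after less exposure. The named contrast therefore mixes two things that Aim 3 wants to separate: accumulation across episodes and the benefit of further recovery nights. If accumulation is present, as the plan predicts, the two pull in opposite directions.

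At stake is how a null result is read. If the plan's conjecture holds, a null on the named contrast could not be taken to mean that extra nights do not help. A significant result in the expected direction would still stand.

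The named contrast also uses recovery days only. The claim it is said to test is a comparison with differences between restriction and recovery days.

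**Working it through.** **Plan's own figure.** The only explicit recovery-sleep row of Table 1 gives −24 ± 28 sec, N=26, paired t-test, α=0.05, power above 0.80. With d = 24/28 = 0.857 and a two-sided test (sidedness is not stated), exact noncentral-t power is 0.987, so the figure reproduces. It describes a cold pressor outcome after two recovery nights, compared with control sleep, in another protocol. It does not apply to either contrast here.

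**Schedule by night.** 3 adaptation/baseline + 9 insomnia + recovery nights 7 and 11 + 4 final recovery nights = 18. The total fits only if the final four are nights 15 to 18, so nights 15 and 17 are the first and third recovery nights after the third episode. The recording nights are then 3, 5, 7, 9, 11, 13, 15 and 17.

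**What the named contrast estimates.** Take insomnia-minus-control levels L, for a marker expected to rise. Let a = L11 − L7, b = L15 − L11 and g = L15 − L17. Then L7 = L15 − a − b, L11 = L15 − b, and

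mean(L7, L11, L15) − L17 = g − (a + 2b)/3.

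With a, b > 0 this is below g. For markers expected to fall, the signs flip and the size of the gain is still understated.

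**Possible size.** The documents give no step sizes, so these are assumptions. Let the steps from baseline be ka, a, a, and let a share f of the day-15 elevation be gone by day 17. Then g = (k+2)af, the shortfall is (a+2a)/3 = a, and shortfall/g = 1/((k+2)f).

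| | f = 1 | f = 2/3 | f = 1/2 |
|---|---|---|---|
| Equal steps (k=1) | 33% | 50% | 67% |
| First step three times the later ones (k=3) | 20% | 30% | 40% |

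The estimate changes sign only if g is below (a+2b)/3.

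**Precision.** With equal variances and independence or compound symmetry, the contrast variance is proportional to 3 × (1/3)² + 1 = 4/3 for the average and 1 + 1 = 2 for day 15 v 17. The standard error ratio (direct/planned) is √(2/(4/3)) = 1.22. With a = b, the two tests have equal power when a/g = 1 − √((4/3)/2) = 0.18. Under AR(1) with two-day correlation 0.3, 0.5 and 0.7 the ratio is 1.10, 0.99 and 0.87.

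**Illustrative power** (N=26, SD 1 per day on the differences, independent days, a = b, two-sided 0.05):

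| a | g | Planned | Day 15 v 17 |
|---|---|---|---|
| 0.4 | 0.6 | 0.14 | 0.55 |
| 0.4 | 0.8 | 0.40 | 0.79 |
| 0.16 | 0.8 | 0.775 | 0.792 |
| 0.1 | 0.8 | 0.84 | 0.79 |
| 0 | 0.8 | 0.92 | 0.79 |

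**Day labels.** The by-night reading is an inference. Assessment of Aim 3 calls days 7, 11 and 15 recovery days, which supports it. The last-minute replacement procedure (B3, before Visit 5) uses adaptation day 1 for the overnight screening and continues next day with adaptation day 2, which puts night 1 after day 1. Carried forward, the daytime samples on day 15 would precede night 15. Days 15 v 17 would then be zero v two recovery nights, and days 7 and 11 would not be recovery days. Assessment of Aim 1 uses days 6, 10 and 14 for insomnia, where the by-night recording schedule gives 5, 9 and 13. The algebra in a and b does not depend on this, but the meaning of g does.

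**The case against.** - **The aim sentence can be parsed another way.** The closing words about the end of the protocol may attach only to the three-night set. A single night could then be any of days 7, 11 and 15, and the average would be a literal implementation. This stands as a reading of that sentence. It does not explain why an expectation stated for days 15 and 17 is tested with a different contrast.
- **The gain can be recovered.** The plan also lists 7 v 11 and 11 v 15, and g = named contrast + (a+2b)/3. The listed contrasts together determine day 15 v 17, and accumulation would show in them. This stands: a reader might infer that the plan cannot estimate the gain, and that is not so. What is missing is a named direct test.
- **Averaging buys precision.** Correct, and a reader might infer from the first power rows that the planned test is the weaker one. That rests on assumed step sizes; the two are about equal at a/g = 0.2 and the order reverses below 0.18.
- **The direction depends on the data form.** Assessment of Aim 1 allows raw values or insomnia-minus-control differences, and the account of the control condition (B3, Visit 3 and 4) reports falling inflammatory markers during control stays. On raw values, a downward drift of c per day adds (17 − 11)c = 6c to the named contrast and (17 − 15)c = 2c to day 15 v 17, which works against the understatement. Control differencing removes drift common to both conditions.
- **The comparison is subordinate.** The main Aim 3 analysis is the four-time-point model, with one against three nights as a further evaluation. That limits the weight of the point but does not remove it.

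**Conclusion.** The point holds in a conditional form. On insomnia-minus-control differences the named contrast estimates g − (a+2b)/3, so it understates the gain from extra recovery nights if one-night recovery worsens across episodes. The size cannot be determined from the documents; under the assumed patterns it runs from 20% to 67% of g. If there is no accumulation there is no understatement, and the named test is then the more powerful one under independence or compound symmetry.

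A separate and firmer finding does not depend on effect sizes: a contrast without any insomnia day cannot test whether the 15–17 difference exceeds every restriction-to-recovery difference. Day 15 v 17 alone would not test that claim either.

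The documents do not support saying that the planned analysis is invalid or sure to lose power. Confidence is moderate, because the reading of days 15 and 17 as first and third recovery nights rests on day labels that the plan does not define and uses inconsistently. The change should be made, but nothing in Aim 3 fails without it.

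**What to change.** 1. First, state for each analysis day which night it follows. Reconcile the last-minute replacement procedure, the recording and blood-sampling schedule, and the day numbers in the Aim 1 and Aim 3 assessments.
2. Then name, as the test of one against three recovery nights, the measurement after the first v the measurement after the third recovery night following the third episode (days 15 and 17 if days are counted by night). Use insomnia-minus-control differences or the equivalent condition-by-day contrast in the mixed model.
3. Keep the average of days 7, 11 and 15 v day 17 as supportive, and keep 3 v 7, 7 v 11 and 11 v 15 for accumulation.
4. Drop the claim that the 15–17 difference is the largest, or test it with difference-of-differences contrasts once the labels are settled.

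On the by-night reading both days are already recording days, so the cost is SAP wording only. If step 1 shows that the day-15 samples precede the first recovery night, the contrast must be tied to whichever measurement does follow that night, or described as what it is. The statistical price is a standard error up to about 1.22 times larger, with lower power if there is little accumulation.

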A total of 34 healthy adults (18-35 yrs, 17 women, including a discontinuation rate of 32%) will be enrolled. Subjects of all racial/ethnic backgrounds will be eligible to participate (see Planned Enrollment Report for expected distributions). Participants will be accepted into the study if they are in good health, do not have an active medical disorder or history of any medical disorders (including sleep disorders), as determined by a medical history, physical screening, and overnight sleep study (PSG, as per methods). Participants from the Boston area, who meet these strict medical eligibility criteria, will be recruited to participate in the 2 x 18-day in-hospital study. Once participants enter the study, they will stay in a patient room at the Clinical Research Center of Beth Israel Deaconess Medical Center. Nurses will check vital signs daily and will assess general emotional and physical well-being at regular intervals throughout each study day. The study physician will also perform an in-person visit with each participant every day, in order to ensure participant's well-being.

Inclusion Criteria:

- Women and men between the ages 18-35 years.
- Non smoking
- Body mass index (BMI) between 18.5 and 30 kg/m².
- For female participants: regular menstrual cycles, no significant discomfort during pre-menses/menses.
- Daily sleep duration between 7-9 hours, verified by REDCap electronic sleep diary.
- Sleep onset within one hour of 11pm (to ensure normal entrainment).
- Blood chemistry in the normal range.
- Medical examination finding within normal range.

Exclusion Criteria:

- Active infection/disease.
- History of neurological, chronic pain, immune, cardiovascular, liver/kidney, or metabolic disorder or Raynaud's syndrome within 6 months prior to study start.
- Active or chronic psychiatric disorders within 6 months prior to study start, including major depressive disorders, bipolar disorders, panic disorders, post-traumatic stress disorders (PTSD), thought disorders, and substance abuse/dependence disorders.
- In psychotherapy or any other behavioral interventions at study start (eg acupuncture for insomnia)

- Sleep disorders.

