- PSG screen results of apnea-hypopnea index (AHI) of >5 events/hour based on PSG screening night, periodic leg movement index (PLMI) >15/hour based on PSG screening night; sleep efficiency <80% based on PSG screening night; restless legs syndrome, circadian rhythm disorders, and nightmare disorders determined by diagnostic interview.
- Pregnant/nursing.
- Regular medication use other than oral contraceptives.
- Donation of blood or platelets 3 month prior to study start.
- Systolic BP measurement <140/90 Hg.
- Use of anti-inflammatory medication one week prior to study start
- Positive urine toxicology screen.
-

Sources of Materials:

Blood, urine, and saliva samples from participants will be assayed for markers involved in the inflammatory and stress response.

Inclusion of Women:

All women of child bearing age who do or do not take oral contraceptives and who are not pregnant or nursing are eligible for the study.

B4. POSSIBLE BENEFITS

This research will not benefit participants directly. However, it will provide important information regarding the effects of repeated exposure to insomnia symptoms on mechanisms responsible for pain amplification. This research is fundamental for the future development of novel strategies targeting specific mechanisms to prevent or reduce pain exacerbated by insomnia

B5. POSSIBLE RISKS AND ANALYSIS OF RISK/BENEFIT RATIO

Side effects related to lack of sleep and maintaining wakefulness for an extended period of time include fatigue, frequent mood changes, increased bodily discomfort such as mild back pain, stomach pain, or headache, as well as nausea and vomiting.

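### The only blood pressure limit in the supplied text is an exclusion criterion that, as printed, rejects volunteers below 140/90 and so contradicts the healthy-volunteer inclusion rules

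*Combined protocol and SAP*

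**What the plan says.** Section C (Subject Selection) sets eligibility in three places that bear on blood pressure.

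- The opening paragraph, under Human Subjects Involvement and Characteristics, describes the population: "Participants will be accepted into the study if they are in good health".
- The Inclusion Criteria require "Medical examination finding within normal range".
- The Exclusion Criteria contain the bullet "Systolic BP measurement <140/90 Hg". They also exclude by history: "History of neurological, chronic pain, immune, cardiovascular, liver/kidney, or metabolic disorder", within 6 months before study start.

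The Exclusion Criteria hold three other measurement limits, all in the polysomnography bullet: "apnea-hypopnea index (AHI) of >5 events/hour based on PSG screening night", "periodic leg movement index (PLMI) >15/hour based on PSG screening night" and "sleep efficiency <80% based on PSG screening night".

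Elsewhere, blood pressure or vital signs appear only as procedures. At Visit 1, nursing staff "will take vital signs and collect a blood sample", with no limit given. The Cardiovascular markers paragraph describes how blood pressure is measured during the stay.

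**The concern.** An exclusion criterion should name the value that disqualifies. Read that way, the blood pressure bullet turns away volunteers below 140/90 and lets through those with both components at or above it. That cannot be squared with a study of healthy adults aged 18 to 35 whose medical examination must be normal.

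Eligibility rules are applied person by person. Staff who follow the bullet as printed act against the inclusion criteria. Staff who do not follow it are using a rule that is not written down. Either way, screening decisions cannot be audited against the protocol.

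The point also touches safety. Section B5 presents extensive screening as a protection, and participants go on to cold-water hand immersion and repeated Valsalva manoeuvres. Sample size, power and the planned analyses are not at stake.

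**Working it through.** No figure in the plan needs reproducing, because no sample size, power or alpha depends on this criterion. The check is one of text and logic.

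**1. Is the bullet an exclusion?** The Exclusion Criteria heading comes after the inclusion list, and no other heading stands between it and the blood pressure bullet. As printed, it is an exclusion.

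**2. How do the other limits in the list work?**

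| Limit as printed | Names the disqualifying value? |
|---|---|
| AHI >5 events/hour | Yes |
| PLMI >15/hour | Yes |
| Sleep efficiency <80% | Yes |
| BP <140/90 | No, given the good-health and normal-examination rules |

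One of four runs the other way. Both inequality signs appear among the first three and both make sense there, so a PDF reading error in the sign is unlikely.

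**3. Does any reading of the bullet as an exclusion remove the conflict?** The bullet says systolic but gives a pair, so three readings are possible: both components below the limit, systolic only, or either component below.

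| Systolic / diastolic | Both below (and) | Systolic only | Either below (or) |
|---|---|---|---|
| <140 / <90 | excluded | excluded | excluded |
| <140 / ≥90 | not excluded | excluded | excluded |
| ≥140 / <90 | not excluded | not excluded | excluded |
| ≥140 / ≥90 | not excluded | not excluded | not excluded |
| Combinations excluded | 1 of 4 | 2 of 4 | 3 of 4 |

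The both-below row is excluded under 3 of 3 readings and the both-at-or-above row under 0 of 3. The two mixed rows change with the reading. The conflict therefore does not depend on how the pair is joined. Changing only the sign, or only the list, would still leave the two mixed rows undecided.

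**4. Does another part of the document settle it?**

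- Visit 1 and B6 (Recruitment): vital signs are taken; no limit.
- Visit 2: physical examination by the study physician; no limit.
- Cardiovascular markers: measurement method only.
- B5 and Subject Protection in B6: both restate the exclusions and name cardiovascular history, without a blood pressure value.

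Nothing in the supplied text gives a second limit.

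**5. Can the number affected be estimated?** No. The document gives no blood pressure distribution. The Participants paragraph anticipates screening 612 people (18 for each of 34 entering the hospital phase, 18 × 34 = 612). B6 places telephone, email and survey screening before the visit at which vital signs are taken, so the number who have blood pressure measured is not stated.

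**The case against.** The strongest reply is that this is an obvious drafting slip. Staff could hardly apply the bullet literally while meeting the inclusion list, so the intended direction can be inferred. Other checks remain: physician review of the first-visit results, a physical examination, exclusion of cardiovascular history, and daily vital signs and physician visits during the stay. Nothing shows that the literal rule was used. This stands, and it limits the practical weight of the point. It does not remove the error: a rule that staff must mentally correct before use should be corrected on paper.

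A second reply is that the bullet may be a required value placed in the wrong list, in which case the conflict disappears. That is one possible correction, not a reading of the bullet where it now stands.

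A third is that the search for another limit is incomplete. Visit 1 cites Appendix 1 for screening tests, and Visit 2 refers to a section on protection of human subjects for detailed exclusion criteria. The appendix is not in the supplied text, and no section there carries that exact title, although section C may be meant. This stands as a limit: the statement that no other blood pressure criterion exists covers the supplied text only.

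Finally, the supplied text does not give enrolment status, so a records check applies only if people were screened under this wording and records were kept.

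**Conclusion.** The concern holds. An operative eligibility rule contradicts the inclusion criteria in the same section, and it does so under all three ways of reading the pair as an exclusion. Two further defects sit in the same bullet: it does not say how mixed systolic and diastolic readings are classified, and its unit is incomplete.

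The conclusion rests on one inference. The document does not define a normal blood pressure, so the conflict is drawn from the plain meaning of good health and normal examination findings. Which limit is clinically right is not judged here.

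The bullet should be corrected, but its effect is limited. The effect on enrolment cannot be quantified. Blood pressure is not among the outcomes in Table 2, and the power calculations and analyses do not change.

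**What to change.** 1. Reconcile the blood pressure bullet with the good-health and normal-examination rules, by settling either the direction of the inequality or the list in which the bullet belongs. The choice is the sponsor's.
2. State the systolic and diastolic components separately, with full units, and say whether they are joined by and or by or, so that mixed readings are classified.
3. If Appendix 1 or any other screening document carries a blood pressure limit, make it agree with the corrected bullet.
4. If people have been screened under this wording and records were kept, confirm from them which rule was applied.

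The cost is a one-line protocol amendment plus the records check. Sample size, design and analysis stay as they are.
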